- **Surgical factors:** The procedure, prior injury, duration of surgery, all perioperative analgesics given and details of participant's prescription and analgesic instructions will be recorded from the medical record.

Study Procedures (SEE TABLE 1 BELOW)

Group assignment: Participants will be randomly assigned a priori by computer generated randomization to one of the three groups: the Control Group (i.e., Routine provider

pen/verbal analgesic instruction), the STOMP written feedback (intervention) Group: (i.e., Routine provider information plus the STOMP written feedback) or the enhanced STOMP Video Feedback (intervention) Group (i.e., Routine provider information plus the STOMP Video feedback).

All baseline and follow-up surveys are completed by the subjects using a Qualtrics survey link via their own smartphone or computer (or our iPad if completed in person) to ensure completeness and privacy. Subjects will enter only an assigned, unique ID number with no other identifying information. STOMP (either written or video groups) will be provided together with each decision exercise (built into the survey itself). The electronic survey includes appropriate logic and prompts to minimize the potential for missing items.

Subjects will be texted/emailed survey links on day 0 (day before or on surgery), day 7, day 14, 1 & 3 months after discharge. Table 1 depicts the study assessments completed at each timepoint. These will be automatically scheduled via our umich gmail system. On each of the survey days, we will also send a text SMS reminder to participants (automated using the same process as our parent study). Subjects can opt to complete surveys via email link (Qualtrics) or via paper/pen (returned via mail). No more than 1 additional text reminder for each will be sent to subjects who have not completed their follow-up surveys.

Sample Size Determination

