Our sample size is based on our recent findings that 26% of adolescents/young adults indicated a willingness to misuse a prescribed opioid for pain management. We need 426 participants (142/group) to detect a clinically important effect of the STOMP intervention on misuse intention (i.e., decrease to 13%; 95% confidence and 80% power). This sample will be more than sufficient to detect an expected mean difference in opioid misuse risk perception between either intervention group and the control (MD 0.56, SD 1.21; sample needed = 122) and to test for a modest effect of the interventions in a factorial design (estimated eta squared 0.14; sample needed = 147). To allow for 30% loss to follow-up and to account for missing data, we will recruit up to 600 participants.

Table 1. Sequence of study assessments

Measures	Time 0 Baseline (preop)	Time 0.1 (Immediately Post-Session)	Time 1 (7 days)	Time 2 (14 days)	Time 3 (1 month)	Time 4 (3 months)
Demographics	x					
Pain, Analgesic and Misuse History	x					
Pain relief Preference	x			x		
Opioid knowledge/ risk perceptions	x	x		x	x	x
Opioid misuse risk perceptions	x	x		x	x	x
Scenario (situational) decision-making	x			x	x	x
Analgesic self-efficacy	x	x				
Pain interference			x	x	x	x
Opioid left-over disposal				x	x	x

Analgesic use and ADEs			x	x	x	x
Perioperative data	x					
Analgesic refill data				x		

DATA ANALYSES

Generalized estimating equations (GEE) will be used to model both continuous (i.e., negative binomial and Gaussian) and binary outcomes (i.e., binomial) for each aim.^{151,152} All models will include both time-varying measures (e.g., opioid risk perceptions) and time-invariant covariates (e.g., sex, race, etc.) and will use either an independent or exchangeable correlation structure to correct for within subject correlations. Analyses will use Stata's (STATA/SE v.13; STATA Corp., College Station, TX) 'xtgee' option as appropriate. All hypotheses per our conceptual model (Figure 3) will be tested at the 0.05 alpha level. Standardized coefficients and adjusted odds ratios will be computed to determine the relative effect size for each of the key independent variables.

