Missing data: The use of electronic surveys with built-in prompts for incomplete items will reduce the potential for missing responses. Patients will be contacted by phone, text or email (per their preference) to promote ongoing recording of postoperative data and to reduce the potential for missing data and LTF. We have used similar procedures to successfully ensure complete data and minimize loss to follow-up.^{8,25,94,153}

Any remaining missing data on surveys (e.g., assist or PR-Pref) will be examined for randomness and we will impute only partial non-response (e.g., missing 1 to 2 items of PR-Pref or assist) using a horizontal (i.e., per individual) approach. Largely incomplete or total survey non-response will be examined for non-randomness and potential bias (e.g., missing DAST-10). These missing data will not be imputed, however, outcomes will be compared for persons with missing vs. complete data to determine selection bias. We have adjusted our sample size to account for the potential for missing data. We will use pairwise deletion to use the available, complete cases to test our hypotheses.

Aim 1: Using GEE, we will examine the association between the STOMP intervention and the outcomes (risk seriousness perception, and situational opioid decisions). It is hypothesized that, compared to controls, patients who receive the STOMP intervention will have 1) enhanced risk perceptions (continuous measure) and 2) improved opioid decisions (scenario-based). Hypotheses 1 and 2 will be tested using both main and interaction effect models. In the main effects models, STOMP group assignment is our binary independent variable of interest. Time by intervention interaction effect models will be used to examine whether the STOMP group has improved opioid risk perceptions and decisions at the follow-up assessments compared to the control group. It is expected that there will be no difference between the intervention group and control group at baseline. However, significant interaction effect terms should emerge for the intervention group at the follow-up assessments.

Anticipated Problems and Solutions:

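### If STOMP messages are interleaved with the Time 0 scenarios, as the text literally reads, the planned time-by-intervention interaction for scenarios 2 to 4 may be biased toward no effect

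*Combined protocol and SAP*

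**What the plan says.** - **Delivery (Study Procedures).** Arms are assigned before the survey is taken, and "STOMP (either written or video groups) will be provided together with each decision exercise (built into the survey itself". The order of saving an answer and showing a message is not stated.
- **Scenarios (Measurements, Opioid decision-making).** There are four: taking more of one's own prescription, using an old prescription, using a friend's prescription, and pain and symptom relief when opioid adverse events are present.
- **Timing (Table 1).** The row "Scenario (situational) decision-making" is marked at Time 0 and Times 2, 3 and 4. It is not marked under "Time 0.1 (Immediately Post-Session". Risk perceptions and self-efficacy are marked in both of the first two columns.
- **Analysis (Data Analyses, Aim 1).** "It is expected that there will be no difference between the intervention group and control group at baseline", while "significant interaction effect terms should emerge for the intervention group at the follow-up assessments". The plan also has main-effects models: "In the main effects models, STOMP group assignment is our binary independent variable of interest".
- **Sample size.** It starts from the finding that "26% of adolescents/young adults indicated a willingness to misuse a prescribed opioid for pain management" and a fall to 13%, with 142 per group.

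**The concern.** The interaction compares the change from Time 0 to follow-up between arms, so it measures the full effect only if the Time 0 answers are untreated. The Time 0 scenario answers are the only baseline for decisions, and they come from exercises to which the messages are attached. If each message appears after its own scenario, the first answer is clean, but the second, third and fourth come after one, two and three messages.

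Any fall that earlier messages produce in the STOMP arms at Time 0 is then subtracted from the follow-up effect. The estimate is diluted for scenarios 2 to 4. Two of these, the old prescription and the friend's prescription, concern misuse intentions of the kind H2 addresses.

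Two related gaps concern the same analysis. If the main-effects model pools Time 0 with follow-up, as the plan appears to intend, it averages in a wave where no effect is expected. And if messages are tied to every exercise, and exercises recur at Times 2 to 4, the follow-up answers would reflect repeated exposure and not persistence of a single session.

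**Working it through.** **1. The text side by side.** Study Procedures attaches STOMP to each exercise. Table 1 places the exercises at Time 0 and has no scenario measure at Time 0.1. Aim 1 treats Time 0 as free of treatment. All three hold together only if the four answers are saved before the first message, and no section says so.

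**2. The plan's own figure.** For 26% v 13%, two-sided 0.05, 80% power, unpooled variance:

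n = (1.960 + 0.842)² × (0.26×0.74 + 0.13×0.87) / 0.13² = 141.9, so 142 per group. This agrees with the plan. It is a simple two-group comparison and does not depend on Time 0.

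**3. Effect on the interaction.** Inputs from the documents: 26%, 13%, 142 per group. Assumptions: these rates apply to the scenario in question (none are given for scenarios 2 to 4), control stays at 26%, and the STOMP Time 0 rate is 26%, 23% or 20%. Since control does not change,

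interaction = logit(0.13) − logit(STOMP Time 0 rate).

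- 26%: −1.901 + 1.046 = −0.855, OR 0.43
- 23%: −1.901 + 1.208 = −0.693, OR 0.50
- 20%: −1.901 + 1.386 = −0.515, OR 0.60

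**4. Power of the interaction.** Wald test on the log-odds scale, with K follow-ups averaged, within-person correlation ρ (assumed) and v(p) = 1/[n p(1−p)]:

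variance per arm = v₀ + v₁(1 + (K−1)ρ)/K − 2ρ√(v₀v₁).

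Example with K = 3, ρ = 0.5, 142 v 142, STOMP Time 0 at 23%:
- Control: v₀ = v₁ = 0.0366, variance 0.0366 + 0.0244 − 0.0366 = 0.0244.
- STOMP: v₀ = 0.0398, v₁ = 0.0623, variance 0.0398 + 0.0415 − 0.0498 = 0.0315.
- SE = √(0.0244 + 0.0315) = 0.2365; 0.693/0.2365 − 1.960 = 0.97; power 83%.

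Power for K = 3 with STOMP Time 0 at 26% / 23% / 20%:

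| ρ | 142 v 142 | 284 v 142 (STOMP arms pooled) |
|---|---|---|
| 0.3 | 88 / 70 / 44% | 95 / 84 / 58% |
| 0.5 | 95 / 83 / 57% | 99 / 93 / 72% |
| 0.7 | >99 / 96 / 78% | >99 / 99 / 90% |

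With a single follow-up, ρ = 0.5 and 142 v 142, power is 82 / 64 / 40%.

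**5. Between-arm comparison at Times 2 to 4.** Time 0 does not enter, so the OR stays at 0.43. Variance per arm is v₁(1 + 2ρ)/3. Power at ρ = 0.3 / 0.5 / 0.7 is 96 / 91 / 86% (142 v 142) and 99 / 98 / 96% (284 v 142).

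**6. Can a Time 0 test settle it?** Comparing 23% with 26% at Time 0 has power of about 9% (142 v 142) or 10% (284 v 142) on the log-odds scale. A non-significant difference is no evidence of a clean baseline.

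**7. Main-effects model.** With equal weights on Times 0, 2, 3 and 4 and a clean Time 0, the STOMP mean is (0.26 + 3×0.13)/4 = 0.1625. The OR against 0.26 is (0.1625/0.8375)/(0.26/0.74) = 0.55, against 0.43 for follow-up alone. With Time 0 at 23% the mean is 0.155 and the OR 0.52.

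**The case against.** A reader might infer that the baseline is contaminated. The documents do not support that. It needs two things that no section states: that messages are shown between scenarios, and that a message about one scenario changes the answer to another. The plan calls the messages feedback, which suggests they follow a response, and Table 1 separates the preoperative baseline from a post-session assessment. The supplement describes mainly its changes from the parent project, so the order may be fixed in the parent protocol or in the survey build. This stands, and it makes the point conditional. It does not remove it: feedback after an answer protects that scenario from its own message, but not from earlier ones. The scenarios and messages are also being modified here, so the order belongs in this plan.

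A second objection is that the harm is modest. This is partly right. Aim 1 treats STOMP as a binary variable, which suggests pooled arms; with Time 0 at 23% and three follow-ups, pooled power stays above the planned 80% at every correlation shown. The main loss is a diluted estimate. Larger carry-over or a single follow-up would cost more.

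Third, not every result would move toward no effect. A partly treated Time 0 would move the pooled main-effects OR slightly the other way, from 0.55 to 0.52. The first scenario, which is closest to the 26% figure, and the Time 0 risk perceptions may well be clean.

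**Conclusion.** The point holds as a conditional one. Taken literally, the delivery text, Table 1 and the Aim 1 model give STOMP participants messages before they answer scenarios 2 to 4 at Time 0. If the messages work in the intended direction and carry over, the interaction for those scenarios is biased toward no effect. The size cannot be derived from the documents. With the assumed rates, a three-point fall at Time 0 moves the OR from 0.43 to 0.50 and power from 95% to 83% (142 v 142) or from 99% to 93% (284 v 142), at correlation 0.5 with three follow-ups.

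It would be wrong to conclude that the sample size is invalid or that the risk-perception results are compromised. The 142 per group reproduces, and risk perceptions have their own Time 0 and Time 0.1 measures.

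The main-effects point does not depend on message order. If Time 0 is pooled in with equal weights and is clean, the OR is diluted from 0.43 to about 0.55.

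**What to change.** 1. **State and lock the order.** Save and lock all four Time 0 scenario answers before any STOMP page opens, and say so in the plan. The interaction can then stand. If the build already does this, it is a text edit; otherwise it is a survey-logic change and a minor amendment. The small downside is looser pairing of exercise and message.
2. **Fallback, only if the survey build shows that answers were interleaved.** Base the scenario test on the randomised between-arm comparison at Times 2 to 4, without Time 0 scenario answers as reference or covariate. Settle the question from the build, not from a baseline significance test. This needs no new data. The cost is some precision: compared with an interaction on a clean Time 0, power goes from 95% to 91% at correlation 0.5, and from over 99% to 86% at 0.7 (142 v 142).
3. **Main-effects model.** Whatever the order, fit it to Times 2 to 4 only. This is a text edit.
4. **Recurrence of messages.** Reconcile Study Procedures with Table 1 on whether messages are shown again at Times 2 to 4. Whether they should be is for the sponsor to decide. If they are, describe follow-up scenario results as repeated exposure; the between-arm comparison does not remove exposure within the same survey.

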Our multidisciplinary team brings expertise in acute post-procedure pain management, adolescent substance use behaviors (with a particular emphasis on prescription opioid misuse among adolescents and emerging adults),^{10,11,22,26,28,43} tailored decision-aid technology and evaluation of educational and behavioral interventions in the clinical setting.⁴⁴⁻⁴⁷ Increasing [name] effort from a consulting role to an active co-investigator will bring a more prominent role regarding effective pain management strategies and interpretation of data.

APPROACH

With this supplement, we aim to expand the target population identified in our parent study to include older adolescents and emerging adults (ages 15-24 years) who are beginning to or are solely making analgesic decisions for themselves following a painful procedure.

We will adapt STOMP messages to specifically address the risks of personal misuse of opioid analgesics and the potential risk of sharing prescribed opioids with others. We will modify the analgesic messages that address safe and effective pain management strategies and early opioid weaning.

Using modified surveys but similar procedures as the parent project, we will test the effect of STOMP on the outcomes: opioid risk perceptions, misuse intentions and behaviors, persistent use and left-over disposal intention.

Expanded sample inclusion and justification: We will recruit up to 600 English speaking patients, aged 15-24 of all races who are expected to receive an opioid prescription for acute, short-term postoperative pain following elective ambulatory or short stay (<48 hrs) orthopedic, sports medicine, or other surgical procedures.

Sample exclusions: We will exclude patients who are undergoing emergency procedures, cannot self-report their pain, have a hematologic-oncologic, kidney or liver condition (precluding the usual analgesic prescription patterns), or who have been recently treated for chronic pain. We will exclude subjects with significant mental health history that includes diagnoses with treatment for severe depression, bipolar disorder, psychoses, suicidal ideation.

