The main potential limitation to achieving our aims is the efficient recruitment of eligible subjects and the potential LTF. Modest monetary incentives will be given for baseline and follow-up surveys which we've found to enhance recruitment rates and minimize LTF in high enrollment studies (\$25 after completion of 1 month follow-up; \$25 after receipt of 3 month follow-up survey).^{95,153} Participants will receive reminders by text, phone or email (per preference) which we have used to successfully reduce LTF and boost return of diaries in our previous longitudinal pain studies.^{8,46,153} We will evaluate our recruitment and retention rates quarterly to determine whether we are on target or whether we need to enhance our recruitment plan.

HUMAN SUBJECTS PROTECTIONS (Same as Parent Project with the following modifications)

For this supplement, we expand our subject involvement to include up to 6005 English speaking adolescents and young adults (ages 15-24) who are prescribed opioids for acute, short-term postoperative pain following elective ambulatory/ short-stay surgical procedures. Males and females of all races will be recruited.

Sampling Plan and Recruitment: Given that adult patients, themselves, are the target population, we will contact potential participants at the time of surgery scheduling, in the preoperative clinic, or by phone or mail prior to the day of surgery to allow ample time to make an informed decision about taking part in the study and to allow time for completion of baseline surveys (prior to surgery). Participants will be provided a verbal synopsis of the study as well as a comprehensive written consent form. Study procedures will not proceed until consent documents are signed.

Potential Risks:

- This study poses no more than minimal risk to participants who are aged 15-24. The primary risk to participants is potential for breach of confidentiality. Given our data collection and handling procedures as outlined in the parent study and re-emphasized below, the potential for breach is extremely unlikely.
- Some adverse effects following surgery and during analgesic use are expected. We will be closely recording all opioid and surgery-related adverse events and will report these per our parent study DSMP and board review.

Protection against risks:

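### At the plan's own 30% loss, recruiting up to 600 retains 420 participants (140 per group), slightly below the stated 426 (142 per group); 600 tolerates at most 29% total loss

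*Combined protocol and SAP*

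**What the plan says.** All references are to the combined protocol and SAP.

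- **Sample Size Determination.** The planning rate comes from the team's survey: "26% of adolescents/young adults indicated a willingness to misuse a prescribed opioid for pain management". The target is a "decrease to 13%; 95% confidence and 80% power". The resulting requirement is "We need 426 participants (142/group) to detect a clinically important effect of the STOMP intervention on misuse intention". The recruitment figure follows: "To allow for 30% loss to follow-up and to account for missing data, we will recruit up to 600 participants".
- **Approach, sample inclusion paragraph.** The same ceiling is given: "We will recruit up to 600 English speaking patients".
- **Human Subjects Protections.** The ceiling appears as "up to 6005 English speaking adolescents and young adults".
- **Data Analyses.** Hypotheses "will be tested at the 0.05 alpha level". The missing-data paragraph says the sample size was adjusted for missing data. It imputes partial non-response only, leaves largely incomplete or absent surveys unimputed, and tests hypotheses on available complete cases. No missing-data rate is given anywhere.
- **Specific Aims.** The team reports its current loss to follow-up as below 15%.

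**The concern.** The recruitment sentence makes a checkable claim: 600 recruits cover 30% loss to follow-up and missing data, and still leave the required number. That does not hold at 30% loss, because 70% of 600 is less than 426. Since 600 is worded as a ceiling, the plan has no stated room to recruit past it.

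What is at stake is the accuracy of the stated 80% power, and whether a reader can tell how much attrition the design was built to withstand. The second matters because participants whose outcome surveys are absent are not imputed, so missing surveys reduce the analysed sample directly.

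**Working it through.** **Inputs.** From Sample Size Determination: control rate 0.26, intervention rate 0.13, 95% confidence, 80% power, 142 per group, 426 in total, 30% loss, ceiling 600. Sidedness is not stated; two-sided 0.05 is assumed because it reproduces 142 and one-sided testing does not (114 per group, or 129 with continuity correction).

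**1. Reproduce the plan's figure.** Unpooled variance, one intervention group against control:

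n = (1.960 + 0.842)² × [0.26 × 0.74 + 0.13 × 0.87] / 0.13² = 7.849 × 0.3055 / 0.0169 = 141.9, so 142 per group and 3 × 142 = 426.

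This matches exactly. The arcsine formula gives 142.1. The pooled-variance formula gives 145 per group (435 in total), and the continuity-corrected one gives 160. The plan's number is therefore a pairwise requirement with no built-in surplus under the formula that reproduces it.

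**2. Apply the plan's loss rate.**

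- Retained from 600: 600 × (1 − 0.30) = 420, or 140 per group. Shortfall: 426 − 420 = 6, or 2 per group (1.4%).
- Recruits needed to retain 426: 426 / 0.70 = 608.6, so 609 (203 per group). The ceiling is 9 below this (1.5%).
- Largest loss 600 can absorb: (600 − 426) / 600 = 174/600 = 29.0%.

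**3. Power for 26% versus 13%.** Unpooled: Φ(0.13/SE − 1.96), with SE = √(0.3055/n). Pooled: Φ((0.13 − 1.96 × SE₀)/SE), with SE₀ = √(2 × 0.195 × 0.805/n).

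| Case | Total | Per group | Unpooled | Pooled |
|---|---|---|---|---|
| Stated requirement | 426 | 142 | 80.0% | 79.3% |
| 600 with 30% loss | 420 | 140 | 79.5% | 78.7% |
| As above, further 5% missing (assumed) | 399 | 133 | 77.4% | 76.6% |
| As above, further 10% missing (assumed) | 378 | 126 | 75.2% | 74.3% |

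The last two rows take missing data as an additional loss among those retained (420 × 0.95 and 420 × 0.90). The rates are illustrations, since the documents give none. Covering them in full would need 426 / (0.70 × 0.95) = 640.6, so 641 recruits, or 426 / (0.70 × 0.90) = 676.2, so 677.

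**4. The team's own experience.** At 15% loss, 600 × 0.85 = 510 remain, 84 above 426.

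**5. A possible source of the figure.** Multiplying instead of dividing gives 426 × 1.30 = 553.8, so 554, which would seem to leave 600 − 554 = 46 for missing data. The documents do not show that this was done. It would not be correct, because 554 × 0.70 = 388.

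**The case against.** The strongest reply is that this is rounding. The gap between 600 and 609 is 1.5%, and power moves by about half a percentage point. The choice of variance formula matters more: pooled and unpooled differ by 3 per group (145 against 142), while the shortfall is 2. That stands, and it sets the severity. But the rounding goes downward, below a requirement the same paragraph states as needed.

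A reader might infer that 600 leaves nothing at all for missing data. The documents do not establish this. The sentence names loss and missing data side by side but gives one rate, so the 30% may be a single reserve for both. Partial item non-response is also limited by survey prompts and, in part, imputed. On the single-reserve reading the additional-loss rows above fall away, but 420 is still below 426.

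A reader might also infer that the trial's main analysis will rest on 420 participants and be underpowered. That goes too far, for three reasons:

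- The analysis is GEE on repeated measures. Table 1 schedules the scenario decisions at 14 days, 1 month and 3 months after baseline, so someone lost after day 14 can still contribute follow-up data. The figure of 420 describes a final-timepoint comparison under 30% loss, not the expected GEE analysis set.
- The Aim 1 analysis describes group assignment as binary. If the two intervention arms are pooled, 280 against 140 gives about 87% power (unpooled) or 90% (pooled variance). With a further assumed 10% missing, 252 against 126 gives 83% or 87%.
- The 30% is about twice the loss the team currently reports. At under 15%, 600 is ample.

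Finally, 6005 is most plausibly a stray digit, and a text-extraction artefact cannot be excluded. It has no bearing on the power arithmetic.

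**Conclusion.** The point holds as an internal inconsistency of minor size. Under the plan's own 30% loss, the ceiling of 600 retains 420 (140 per group) and not 426 (142 per group); 600 supports at most 29.0% total loss. For one intervention group against control at the final timepoint, power is about 79.5% (unpooled) or 78.7% (pooled) where 80% is stated. If missing data are additional to the 30%, it is lower: about 77% with an assumed extra 5%.

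This rests on two-sided testing at 0.05, equal allocation, a pairwise comparison, and lost participants contributing nothing to that comparison. It does not show that the trial is underpowered: GEE uses the earlier follow-ups, a pooled-arm comparison would exceed 80%, and loss near the team's reported level would leave about 510. The differing ceilings of 600 and 6005 are a separate clerical matter.

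**What to change.** Restate the recruitment sentence and keep 600. Either wording is enough:

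- 600 covers up to 29% combined loss to follow-up and missing data, leaving 426 (142 per group); or
- 30% loss leaves 420 evaluable (140 per group), with about 79% power for each pairwise comparison at the final timepoint.

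Whichever is chosen, say explicitly whether the loss rate includes missing outcome surveys, and make the statement in the missing-data paragraph agree with it. In Human Subjects Protections, reconcile 6005 with 600.

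The cost is wording only: no added participants and no change to the analysis, at the price of a stated loss tolerance or power about one point less favourable.
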